## 6.3 Statistical Methods

### 6.3.1 Group Allocation Flow Chart for Phase IIB

[figure not shown]

Figure 8: Group Allocation Flow Chart (Phase IIB)

### 6.3.2 Baseline Data

R Statistical Software (Vienna, Austria) and G\*Power version 3.1.9.2 (Düsseldorf, Germany) will be used for data analysis. Prior to performing analyses, standard data cleaning Interventions will be applied. These Interventions include: screening the data for data-entry errors, checking for outliers, assessing the extent and pattern of missing data, and checking that appropriate assumptions of normality are met whenever necessary. Exploratory assessments will include the influence of covariates (i.e., the clinically relevant variables to be recorded) on outcome measures. Graphical displays, as appropriate, will be included as part of data analysis.

Baseline and demographic characteristics and other data will be summarized by standard descriptive summaries (e.g., means and standard deviations for continuous variables such as age, and percentages for categorical variables such as gender).

### 6.3.3 Primary Objective Analysis

Data from Phase I and Phase IIA will be observational and will not test a hypothesis. Data on feasibility and tolerability from Phase I and data on EAD(P) patency restoration will be reported as counts and percentages.

In Phase IIB, the primary objective is efficacy comparison between TubeClear® intervention and CHOP Standard Treatment. EAD(P) patency restoration will be measured by the ability to flush the EAD(P) with 10 ml of air within five (5) minutes following the Intervention. Efficacy is the proportion of EAD(P)s restored to patency in each group. A chi-square analysis (or Fisher's exact test) will be performed to compare the efficacy of TubeClear® intervention to the CHOP Standard Treatment. Intention-to-treat analysis will be used to compare the efficacy of the TubeClear® intervention to the CHOP Standard Treatment. Patients will be analyzed according to their randomized allocation. Full reporting of any deviations from random allocation and missing responses will be recorded and assessed in accordance with the CONSORT guidelines. Exploratory-per-protocol analysis will also be reported.

#### **6.3.4 Secondary Objective Analysis**

Data from Phase I and Phase IIA will be observational and will not test a hypothesis. Data on 1) pain, using established age-appropriate pain scales, 2) physiologic changes in vital signs, 3) distress related EAD(P) events, and 4) adverse events related to TubeClear® use will be described and reported as counts and percentages.

In Phase IIB, the secondary objectives between TubeClear® intervention and CHOP Standard Treatment include comparison of 1) time to intervention, 2) pain using established age-appropriate pain scales, 3) physiologic changes in vital signs, 4) distress related EAD(P) events, and 5) adverse events related to either group.

1. A log-rank test will be performed to compare intervention time of TubeClear® intervention to the CHOP Standard Treatment.
2. A Wilcoxon rank sum test will be performed to compare differences in subject pain and discomfort between TubeClear® intervention and CHOP Standard Treatment.
3. A t-test will be performed if the distributions are normal (or non-parametric equivalent, if the distributions are not normal) to compare differences in physiologic changes (i.e. vital sign changes) between TubeClear® intervention and CHOP Standard Treatment.
4. A Wilcoxon rank sum test will be performed to compare differences in distress related EAD(P) events (i.e. subject behavior such as pulling/yanking) between TubeClear® intervention and CHOP Standard Treatment.
5. A chi-square analysis (or Fisher's exact test) will be performed to compare the proportions of adverse events (i.e., EAD(P) displacement from the intervention; EAD(P) damage from the intervention; any enteral tract tissue perforation from the intervention) in TubeClear® intervention and CHOP Standard Treatment.

Intention-to-treat analysis will be used to compare the secondary endpoints between the TubeClear® intervention and the CHOP Standard Treatment. Patients will be analyzed according to their randomized allocation. Full reporting of any deviations from random allocation and missing responses will be recorded and assessed in accordance with the CONSORT guidelines. Exploratory-per-protocol analysis will also be reported.

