**ABBREVIATIONS AND DEFINITIONS OF TERMS**

AE	Adverse Event
Pain Scales	
Include but are not limited to:
 
Face, Legs, Activity, Cry, Consolability (FLACC)  - <math>\geq</math> 7 years of age; may be used in the older child
 
Revised Face, Legs, Activity, Cry, Consolability (rFLACC)  - <math>\geq</math> 7 years of age; may be used in the older child
 
FACES Pain Scale Revised (FPS-R)  - <math>\geq</math> 3 years of age; may be used in the older neurologically impaired, non-verbal child
 
Numeric Pain Scale  - <math>\geq</math> 8 years of age; cognitively intact patients, able to self-report

AMI	Actuated Medical, Inc.
BMI	Body Mass Index
BSA	Body Surface Area
CHOP	The Children's Hospital of Philadelphia
DOB	Date of Birth
EAD	Enteral Access Device
J	Jejunostomy Tube
ND	Nasoduodenal Tube
NG	Nasogastric Tube
NJ	Nasojejunal Tube
AMT GJ	Applied Medical Technology, Inc. Gastrojejunral 14 Fr Tube
EAD(A)	Adult Feeding and Decompression Access Device ND, NG, NJ, G, and J Tubes of size 10 – 18 Fr, 10 – 140 cm
EAD(P)	Pediatric Enteral Access Device ND, NG, and NJ 6 – 8 Fr, 38 – 140 cm; and NG tube (Corflo, Corpak MedSystems) used as a J tube inserted through a G tube 6 – 8 Fr, 38 – 140 cm; GJ tube (AMT) 14 Fr, 38 – 140 cm (15 – 55 in)
EAD(P) Adverse Event	EAD displacement, EAD damage, enteral tract tissue injury

EHR	Electronic Health Record
EPIC	Integrated Electronic Health Record system used at The Children's Hospital of Philadelphia
Fr	French gauge (conventional unit of measure used to describe tube diameter size (1 Fr = 0.33 mm))
IR	Interventional Radiology
MRN	Medical Record Number
MUSC	Medical University of South Carolina
NIH / NICHD	National Institutes of Health / National Institute of Child Health and Human Development
PCU	Progressive Care Unit
PICU	Pediatric Intensive Care Unit
SBIR	Small Business Innovation Research
Tube	Feeding tube
USA	United States of America

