### **General overview of Study Treatment Phase – Phase IIB**

- Female patients  $\geq$  10 years of age or those who have experienced the onset of menses must have a documented NEGATIVE pregnancy test (urine or blood).
- Subject will be randomized to either TubeClear® intervention (experimental) or CHOP Standard Treatment (control) group according to randomization sequence.
- Subject's most recent radiograph will be obtained and reviewed by the Investigator to identify EAD(P) characteristics and tube tip location, as well as pre-existing abnormalities, including damage to EAD(P) and/or tissue, if any.
- The Investigator has the option to order a new radiograph prior to the intervention if there is uncertainty about the status of the EAD(P) tube tip location and characteristics.
- The Subject's Nurse will obtain standard baseline measures of Subject pain.
- Subject will receive TubeClear® intervention or CHOP Standard Treatment based on the randomization assignment.
- If randomized to TubeClear®, EAD(P) length will be determined by review of Subject's EHR and/or markings on the EAD(P). The Investigator will place the Operator-set Collar to the same length determined by review of Subject's chart and/or markings on the EAD(P). The TubeClear® Instructions for Use (i.e., Operator's Manual) will be followed by the user to restore patency to the EAD(P).
- If randomized to CHOP Standard Treatment, the CHOP protocol to restore patency to occluded EAD(P) will be followed.
- Data will be gathered or abstracted from the EHR prior to, during the Subject receiving either intervention, and through the follow-up period. This data includes subject name, date of birth, contact information for parent/guardian, age, sex, ethnicity, weight, stature, BMI, location (PICU/PCU/IR), dates of hospitalization (length of stay),

medical record number (MRN), contact serial number (CSN), diagnosis, procedures performed, medications administered, laboratory and radiology results, ventilator parameters (if ventilated), severity of illness, nutrition information, information on EAD and clog, and physical assessments with vital signs (patient temperature, heart rate, respiratory rate, blood pressure and pain level).

- Nursing assessment using the appropriate scale of the Subject's pain prior to and following the respective intervention will be abstracted from the medical record.

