### **5.1.6 Other Evaluations, Measures**

Portable abdominal radiograph with contrast agent after intervention (and portable abdominal radiograph, prior to intervention, if needed).

Clinical Patient Assessment Measurements (i.e., pain, feeding tolerance, and usual measures to determine EAD(P) location) will be performed prior to, immediately following, and for up to three (3) days after all interventions. Patients who are discharged from the hospital prior to three days will be followed up daily by phone for Clinical Assessment Measurements i.e., pain, feeding tolerance and EAD(P) location as assessed by caregiver until post intervention day three.

Age Appropriate Pain Scale Assessments (these scales include, but are not limited to): Face, Legs, Activity, Cry, Consolability (FLACC) Scale; Revised Face, Legs, Activity, Cry, Consolability (rFLACC) Scale; FACES Pain Scale revised (FPS-R); Numeric Pain Scale; Nursing judgment

Behavioral Likert scale and Generic Behavioral Analysis developed in conjunction with The Food and Drug Administration (FDA) will be used to assess subject behaviors during the study intervention. The Behavioral Likert Scale will be used by the study investigators to objectively assess subject behavior, while the Generic behavioral Analysis consists of questions that will be administered by the study investigators to the subject and their parent/guardian to assess their subjective assessment of the study intervention.

EAD(P) air and water flush.

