In Phase IIB, Subject pain will be assessed before and after use of either intervention using established age-appropriate pain scales. Acute changes in physiologic parameters will be measured, including changes in heart rate, blood pressure and respiratory rate. Distress related EAD(P) events which may be manifested by pulling or yanking of the EAD(P) will be monitored in relation to either intervention. Following either intervention, each Subject will receive an abdominal radiograph with contrast. Study procedures carried out in IR may utilize low-dose fluoroscopy as an alternative to the portable abdominal radiograph. Radiographs will be reviewed by a radiologist (blinded to the study) for EAD(P) adverse events (i.e., EAD(P) displacement, EAD(P) damage, enteral tract tissue injury) attributable to either intervention. Incidence of adverse events attributable to the intervention (i.e. EAD displacement, EAD damage, enteral tract tissue injury) following the intervention will be monitored and reported in both groups.

In all phases, surveillance will include daily assessment for adverse events related to the respective study intervention (i.e. subject pain, feeding intolerance, EAD(P) displacement, EAD(P) damage, enteral tract tissue injury) and will continue for three (3) days. Patients who are discharged from the hospital prior to 3 days will be followed up daily by phone until completion of 3 days following study interventions.

1. Intervention time (measured in minutes) is the time interval between commencement of intervention and achievement of EAD(P) patency (if successful).
2. Physiological parameters will be recorded from the Subject's EHR.
3. Distress related EAD(P) events which may be manifested by pulling or yanking of the EAD(P) will be monitored and recorded by Research Personnel or the Subject's nurse.

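### The Phase IIB pain test leaves its outcome undefined and does not build in the pre-intervention score, so it will generally have less power than a baseline-adjusted rank analysis

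*Combined protocol and SAP*

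**What the plan says.** Section 6.3.4, item 2, gives the whole of the Phase IIB pain analysis: "A Wilcoxon rank sum test will be performed to compare differences in subject pain and discomfort" between the two arms. It names no covariate, stratum, time point or rule for combining scales.

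Pain is measured on both sides of the intervention. Section 6.2 says "Subject pain will be assessed before and after use of either intervention using established age-appropriate pain scales". The Phase IIB overview in section 4.2 says "The Subject's Nurse will obtain standard baseline measures of Subject pain", and adds that nursing pain assessments "prior to and following the respective intervention will be abstracted from the medical record".

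Several instruments are allowed. Section 5.1.6 opens its list with "Age Appropriate Pain Scale Assessments (these scales include, but are not limited to" and names FLACC and rFLACC, then "FACES Pain Scale revised (FPS-R); Numeric Pain Scale; Nursing judgment". In the abbreviations table the Numeric Pain Scale is for children from "8 years of age; cognitively intact patients, able to self-report", while the FLACC scales and FPS-R may be used in some older children. More than one instrument can therefore apply between 11 and 17 years.

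The only provision for covariates is in section 6.3.2, which plans exploratory assessments of covariate influence without naming a variable, model or endpoint.

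**The concern.** Two things are left open. First, *differences in subject pain* could mean a difference between arms in post-intervention scores, or a difference between arms in pre-to-post change. The neighbouring items do not settle it. Item 3 speaks of changes for vital signs, whereas item 4 uses the same *differences* wording for distress events, which have no baseline. That leans towards post scores but is not conclusive. The time point is also open, because pain is assessed immediately afterwards and for up to three days (sections 3.1.3 and 6.3.6).

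Second, neither reading uses the baseline score well. A post-score test discards it. A change-score test subtracts it in full, which adds noise when the correlation between the two readings is modest.

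At stake is a stated secondary objective in a comparison of 17 against 17. A result showing no difference in pain could reflect low power, and the choice between readings could be made after the data are seen.

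**Working it through.** **The plan's own figure.** Pain has no power statement; section 6.4 sizes the trial on patency, 95% against 50%. Enumerating the two-sided Fisher exact test at alpha 0.05 gives 77.7% power at 16 per arm and 81.3% at 17. The 17 per arm reproduces and is taken as given.

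**Inputs for pain.** From the documents: 17 per arm and alpha 0.05 (sidedness not stated; two-sided assumed). Assumed, because the documents do not give them: a between-arm effect d of 0.8 SD, equal SDs before and after, and a pre-post correlation ρ of 0.3 to 0.7.

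**Formula.** Under normality the Wilcoxon test has efficiency 3/π, so the effective n is 17 × 3/π = 16.23 per arm. The standard error of the arm difference is √(2/16.23) = 0.351 SD. Power is approximately Φ(d/(0.351 × s) − 1.96), where s is 1 for post scores, √(2(1 − ρ)) for change and √(1 − ρ²) with baseline adjustment.

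Example at ρ = 0.3, with 0.8/0.351 = 2.279:
- post: Φ(2.279 − 1.96) = 62.5%
- change: s = √1.4 = 1.183, so Φ(1.926 − 1.96) = 48.7%
- adjusted: s = √0.91 = 0.954, so Φ(2.389 − 1.96) = 66.6%

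| ρ | Post-score Wilcoxon | Change-score Wilcoxon | Baseline-adjusted | Gain over post | Gain over change |
|---|---|---|---|---|---|
| 0.3 | 62.5% | 48.7% | 66.6% | 4.1 | 17.9 |
| 0.5 | 62.5% | 62.5% | 74.9% | 12.4 | 12.4 |
| 0.7 | 62.5% | 83.7% | 89.1% | 26.6 | 5.4 |

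At ρ = 0 the adjusted s equals 1, so the gain over post scores is zero. The unadjusted post-score test reaches 80% power only at d = (1.96 + 0.842) × 0.351 = 0.98 SD.

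**Simulation, one instrument, rounded 0–10 scores.** With 3,000 trials per setting and d = 0.8:
- ρ = 0.3: post 56.3%, change 43.9%, rank ANCOVA 59.6% (gains 3.3 and 15.7 points)
- ρ = 0.5: post 58.4%, change 57.7%, rank ANCOVA 68.7% (gains 10.3 and 11.0 points)

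A second set assumed SD 1.8 and a 1.5-point effect (1.5/1.8 = 0.83 SD), with ρ = 0/0.3/0.5:
- mid-range scores: rank ANCOVA on baseline alone 63/67/70%, post 60–63%, change 37/50/61%
- many scores at zero: rank ANCOVA 55/57/63%, post 54–56%, change 38/46/59%

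The smallest gain over change, 63 − 59 = 4 points, comes from this last case. There the gain over post scores at ρ = 0.3 is only 1 to 3 points.

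**Scale.** With two instruments and 20–40% of children on the second, stratifying the post-score test by scale moves power by −2 to +2 points if the instruments differ in level by 0 to 0.5 SD, and by +4 to +8 points if they differ by 1 SD. When scales agree, a scale term costs about 2 to 4 points.

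**Type I error.** Simulated rates were 3.8% to 5.8% across all methods, the planned one included.

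**The case against.** The strongest reply is that the plan may already use the baseline. Pain is assessed before and after, so *differences* can be read as pre-to-post change, and a change score also cancels a constant offset between scales if the same scale is used both times. That stands as far as it goes: a reader might infer that the plan ignores baseline pain, and the text does not establish that. What remains is that the variable is undefined and that adjustment generally does better than either candidate.

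A reader might also infer that pooling scores from different instruments is itself a demonstrated loss of power. The documents do not support that. They give neither the mix of scales nor any difference in level between them, and the loss is close to nil unless instruments differ by about 1 SD. With about 65% zeros and equal scales, a model with baseline and scale terms gave 43–51% power against 47–49% for the post-score Wilcoxon test at correlations of 0 to 0.5. That is a reason not to put a scale term in the main analysis. Pooled ranks across observer, self-report and judgment scores are still harder to interpret.

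Section 6.3.2 does promise exploratory covariate work, but it does not alter the test named in 6.3.4. Finally, pain is one of five Phase IIB secondary comparisons, and power is claimed only for primary endpoints. That is correct and limits the weight of the point.

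**Conclusion.** The point holds as a low-priority improvement. The pain outcome and its time point should be defined, and the recorded pre-intervention score should enter the test. On illustrative assumptions (17 per arm, effect about 0.8 SD, correlation 0.3 to 0.5) baseline adjustment adds roughly 3 to 12 points of power over a post-score Wilcoxon test and 4 to 18 over a change-score one. The gain over post scores shrinks to about zero as the correlation approaches zero, and is at or below the bottom of its range when many scores are zero and the correlation is 0.3. No setting examined showed a material loss from adjusting for baseline alone.

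It would be wrong to conclude that the planned test is invalid: randomization protects its type I error. Nor does anything here touch the patency comparison or the sample size.

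**What to change.** In section 6.3.4, item 2:
- Define the outcome as the pain score immediately after the intervention.
- Compare arms by rank ANCOVA: regress the rank of that score on arm and on the rank of the pre-intervention score, and test the arm term.
- Require the same scale before and after within a child, and record which scale was used.
- As a sensitivity analysis, adjust for or stratify by scale type in two groups, observer-rated (including nursing judgment) and self-report. Two groups keep the cells usable with 34 children. State how a nursing-judgment entry is scored for ranking, since section 5.1.6 lists it without a numeric form.

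The cost is SAP wording, one data field naming the scale, and a short instruction to the nurses and abstractors. No extra assessments are needed. The main analysis spends one degree of freedom on baseline pain; the 2 to 4 points that a scale term would cost if scales agree fall only on the sensitivity analysis.

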### **6.3.6 Safety Analysis**

All Subjects entering the Study will be included in the safety analysis. Clinical Patient Assessment Measurements (i.e., pain, feeding tolerance, and usual measures to determine EAD(P) location) will be performed prior to, immediately following, and for up to three (3) days after all Interventions. Clinically significant changes will be addressed and managed by the Subject's medical team, but recorded, reported, and followed by the Study team. Surveillance will include assessment for any adverse event(s) related to the intervention (i.e. EAD(P) displacement, EAD(P) damage, enteral tract tissue injury) and will continue for up to three (3) days following interventions in either group. Patients who are discharged from the hospital prior to three days will be followed up daily by phone for Clinical Assessment Measurements i.e., pain, feeding tolerance and EAD(P) location as assessed by caregiver until post intervention day three.

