## 8 SAFETY MANAGEMENT

### 8.1 Clinical Adverse Events

Clinical adverse events (AEs) (any unfavorable and unintended sign including an abnormal finding, symptom or disease associated with the use of a medical intervention, regardless of whether it is considered related to the medical intervention, that occurs during the course of the Study) will be monitored throughout the Study. While no clinical adverse events are anticipated, potential adverse events include:

- Clearing Stem exits the distal end of the EAD(P) and punctures the intestinal mucosal membrane.
- Clearing Stem causes damage to the EAD(P) that requires replacement of the EAD(P).
- A possible clinical adverse event for either intervention would be that the occluded medication is bolus flushed into the Subject's digestive system when patency is restored. The medication will have a varying rate of absorption in the digestive system that may cause unanticipated side effects to the Subject depending on the medication's safe therapeutic range. However, when using the TubeClear® occlusion clearing procedure (**Figure 4**) (i.e., an iterative process of partially clearing the occlusion then aspirating the broken occlusion particles, repeating until the collar reaches the EAD external ports (**Figure 2B**) would minimize potential for this clinical adverse event. Since the medication is periodically aspirated from the EAD(P), the final EAD(P) patency flush should contain minimal medication.
- The contrast used in the post-intervention radiograph could result in an allergic reaction to contrast agent. The post-intervention radiograph will also incur a dose of radiation. However, this dose replaces the dose that would be received for EAD(P) replacement if the occlusion was not cleared.

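### The Phase IIB adverse-event comparison (6.3.4 item 5) uses a shorter event list than the surveillance in 2.2 and 6.2, so feeding intolerance and non-perforating tissue injury have no named between-arm comparison

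*Combined protocol and SAP*

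**What the plan says.** - **Surveillance list, all phases (Sections 2.2 and 6.2).** Intervention-related adverse events are assessed daily; the list reads "i.e. subject pain, feeding intolerance, EAD(P) displacement, EAD(P) damage, enteral tract tissue injury) and will continue for three (3) days".
- **Phase IIB sentence in the same Section 6.2.** A shorter list is to be monitored and reported in both groups: "Incidence of adverse events attributable to the intervention (i.e. EAD displacement, EAD damage, enteral tract tissue injury) following the intervention".
- **Glossary.** An EAD(P) adverse event is defined by three items: "EAD displacement, EAD damage, enteral tract tissue injury".
- **Phase IIB comparison (6.3.4 item 5).** The objective is worded broadly, as adverse events related to either group. The test is then restricted by an i.e. list: it is used "to compare the proportions of adverse events (i.e., EAD(P) displacement from the intervention; EAD(P) damage from the intervention", and the last entry is "any enteral tract tissue perforation from the intervention".
- **Other Phase IIB secondary tests (6.3.4 items 1 to 4).** Intervention time, pain, vital signs and distress-related tube events.
- **Safety analysis (6.3.6).** "Clinical Patient Assessment Measurements (i.e., pain, feeding tolerance, and usual measures to determine EAD(P) location) will be performed" before, immediately after and for up to three days after intervention. Clinically significant changes are recorded and reported. No between-arm comparison is named.

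**The concern.** Item 5 is the only planned between-arm analysis of adverse events, and its list is closed. Followed as written, it can yield a statement that adverse events did not differ between arms when two kinds of event on the plan's own daily list were never compared. Non-perforating injury is the more direct device harm: Section 1.3.1 reports localised lesions without full puncture when the stem was over-inserted in the live animal model. A test confined to perforation would not count that kind of finding in a child.

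Section 9.5 says that the data may go into an FDA premarket notification, and Section 9.1.2 says that investigators and research staff are not blinded. If the choice of what to compare is left until results are visible, it becomes a post hoc choice.

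**Working it through.** **1. The lists side by side**

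| Event | 2.2 and 6.2, all phases | 6.2 Phase IIB sentence; glossary | 6.3.4 between-arm comparison |
|---|---|---|---|
| Pain | yes | no | item 2 (Wilcoxon rank sum) |
| Feeding intolerance | yes | no | none |
| Tube displacement | yes | yes | item 5 |
| Tube damage | yes | yes | item 5 |
| Tissue injury | yes | yes | item 5, perforation only |

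Of the five events under daily surveillance, item 5 compares two in full and one in part. Item 2 covers a fourth. The fifth, feeding intolerance, appears in none of items 1 to 5. Non-perforating injury drops out under either source list, because both say injury.

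**2. The plan's own figure.** No figure is given for the adverse-event test. The Phase IIB size of 17 per arm (Section 6.4) comes from patency rates of 95% and 50%, alpha 0.05 and power of at least 0.8. Taking a two-sided test (the text does not state sidedness):

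- n = [1.96·√(2·0.725·0.275) + 0.842·√(0.95·0.05 + 0.50·0.50)]² / 0.45² = (1.238 + 0.459)² / 0.2025 ≈ 14.2, so 15 per arm; 19 with continuity correction.
- Exact power of Fisher's test, by full enumeration: 0.777 at 16 per arm and 0.813 at 17.

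So 17 reproduces, and it is the size available for safety.

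**3. What 17 per arm can show for an added event.** With no events in one arm and k in the other, the two-sided Fisher p-value is 2·C(17,k)/C(34,k):

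- k = 4: 2·2,380/46,376 = 0.103
- k = 5: 2·6,188/278,256 = 0.044
- k = 6: 2·12,376/1,344,904 = 0.018

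The documents give no feeding-intolerance rate, so the rates below are assumptions that show a range (two-sided Fisher, 0.05, 17 per arm):

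| Assumed rates | Power |
|---|---|
| 5% vs 20% | 0.12 |
| 5% vs 30% | 0.35 |
| 5% vs 40% | 0.61 |
| 10% vs 40% | 0.39 |
| 20% vs 50% | 0.32 |

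Even 0 events in 17 leaves an exact two-sided 95% upper limit of 1 − 0.025^(1/17) = 0.195, or about 20%. A p-value would say little here; counts and an interval say more.

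**The case against.** The strongest reply is that item 5 follows the three-event list. The Phase IIB sentence in 6.2, the glossary and the surveillance sentence in 6.3.6 all use that list, and several procedural sections repeat it. Feeding tolerance is handled as a clinical assessment measurement, collected before and after intervention in both arms, with significant changes reported. At 17 per arm, descriptive safety reporting is a defensible choice.

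Much of this stands. A reader might infer that the plan drops a defined Phase IIB endpoint or ignores feeding intolerance; the documents do not support that, since the Phase IIB sentence omits it and 6.3.6 still measures it. What does not stand is that the plan is therefore consistent. Section 6.2 carries two different lists, and item 5 departs even from the shorter one by replacing injury with perforation.

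Three other inferences go too far:

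- **That Standard Treatment interrupts feeds for four hours.** Section 3.3.1 estimates treatment time including preparation and does not mention feeds. A mechanism by which one arm would have more feeding intolerance is not established. The water added with TubeClear is followed by aspiration in each cycle (Section 1.2), and children who cannot tolerate the flush volume are excluded.
- **That feeding intolerance is the only gastrointestinal event followed daily.** Tissue injury is on the same list.
- **That the event in 8.1 in which "occluded medication is bolus flushed into the Subject's digestive system when patency is restored" needs its own test.** It is named as a possible event for either intervention, but no daily assessment of it is listed, and medication recording under Section 4.5 stops at the end of the intervention.

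**Conclusion.** The point holds as an inconsistency between lists that leaves a gap in the planned comparison. One of the five events under surveillance (feeding intolerance) and the non-perforating part of another (tissue injury) have no named between-arm comparison in Phase IIB, although both are assessed through day 3. Collection and reporting are not in question, and the primary patency analysis is unaffected.

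The conclusion rests on reading i.e. in item 5 as closing the list. The likely size of any difference between arms cannot be stated, because the documents give no event rates; the powers shown depend on assumed rates and indicate only that precision will be low.

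**What to change.** 1. Use one adverse-event list in 2.2, 6.2, 6.3.4 and 6.3.6, and bring the glossary and the anticipated-event list in 5.4 (which names tube perforation where the others have tube damage) into line with it.
2. In 6.3.4 item 5, replace perforation with injury. Add feeding intolerance through day 3 and any adverse event, saying whether pain, already compared in item 2, counts towards the latter.
3. Report each by arm as counts with the risk difference and an exact 95% confidence interval, labelled descriptive.
4. State how feeding intolerance is judged to be an event, and whether the unit is the child or the occlusion episode. Section 3.1.1 allows up to three enrolments, and an exact interval that treats every episode as independent would ignore repeat episodes in one child.
5. Report effects of flushed medication descriptively if they occur, with no separate test.

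The cost is a short amendment to the text plus the event definition and the unit rule. Feeding tolerance and tissue injury are already assessed in both arms, so no new data collection is needed for them. The downside is a few more secondary comparisons with wide intervals at 17 per arm.
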